## **Recruitment**

Participants will be recruited via media recruitment methods (e.g., social media, UW-CTRI website, TV, and earned media) from Madison and Milwaukee, WI. Additionally we will proactively ask current participants in this study to recruit their friends with approved fliers and business cards. Interested smokers will call the study phone number or click the web links in

recruitment advertisements. Web recruitment will direct to a UW-CTRI website that provides basic information about the study goals, treatment offered, participant requirements, and financial compensation. Participants may provide their telephone and/or mailing address contact information (via voicemail or UW Qualtrics website or REDCap website) for study staff to return their calls and screen them for eligibility. Potentially eligible participants will be scheduled to attend an in-person, Orientation Visit. Participants who are potentially eligible but do not attend the Orientation Visit will be re-contacted to invite them to reschedule if they remain interested.

### **Study Visits and Phone Contacts: Orientation, Precessation, and Cessation Phases**

For Study Visit and phone contact schedule and procedures see Table 1 (Orientation, Precessation) and Table 2 (Cessation). Participants will receive one visit-reminder (call, email, and/or text) prior to each study visit.

#### **Orientation Phase (TQD >-2 weeks)**

*Orientation Visit 1 (TQD >-2 weeks).* Participants will be provided an overview of the study goals and procedures in an individual setting. They will then be presented a written consent form and their questions will be answered. Interested participants will sign the consent form. Following successful consent, participants will be screened for eligibility (e.g., questionnaires, blood pressure, expired breath CO sample). Participants will provide urine nicotine/cotinine samples and complete a computerized self-report assessment battery (via REDCap and/or Qualtrics, see Table 1). Participants will schedule their TQD and the various study visits/calls. Participants will be instructed how to complete smartphone ecological momentary (EMA) mobile assessments on their own phone. Participants will be asked when they would prefer to receive assessment calls and will be given a calendar that shows all the study calls, visits, and assessments required by the study as well as contingent incentive amounts.

#### **Precessation Phase (TQD -2 weeks to TQD)**

There will be three phone contacts during the Precessation Phase.

*Precessation Call 1 (TQD -2 weeks).* Participants will engage in mobile assessments daily for 2 weeks during the Precessation Phase (EMA starting TQD-14d) while smoking ad libitum and prior to any pharmacotherapy treatment. The Precessation Call 1 will occur approximately 2 days after the start of EMA (TQD-12 days) to address any EMA problems (e.g., adherence or technical troubleshooting). Participants will complete a brief self-report assessment battery during this call.

*Precessation Call 2 (TQD -1 week).* Participants will receive smoking cessation counseling and complete self-report assessments at this phone call. This call will also involve dealing with any smartphone data assessment issues that arise during the Precessation Phase and instruction to continue mobile assessment for the next 1 week until the TQD.

*Precessation Call 3 (TQD -1 to -3 days).* This call will focus on preparing the participants for the TQD, reminding them of its date, and stressing the importance of complete abstinence after the TQD. Participants will complete the self-report assessments. This call will also address any EMA problems (e.g., adherence or technical troubleshooting).

#### **Cessation Phase (TQD to +10 weeks)**

Participants will attend 2 study visits and 3 study calls during this phase.

*Cessation Call 4 (TQD Day +1-2).* Participants will receive smoking cessation counseling, complete self-report assessments including any smoking since their TQD. Participants will be reminded to attempt to completely abstain from smoking and use of all nicotine products. Mobile assessment data will be reviewed and problems with collection of such data will be addressed.

*Cessation Visit 2 (TQD Day +7).* Participants will receive smoking cessation counseling, complete self-report assessments including any smoking since their last visit, and provide breath CO and urine nicotine/cotinine samples. Participants will be reminded to attempt to completely abstain from smoking and all nonmedicinal nicotine products. Participants will be provided with an 8-week supply of C-NRT including nicotine patches and nicotine mini-lozenges with instructions on how to use them (through TQD +9 weeks). Participants will be encouraged to start the medication the following day and to use their medication adherently. Mobile assessment data will be reviewed and problems with collection of such data will be addressed. If a participant is unable to attend Visit 2 or Visit 3 (2 weeks post-quit; described below) we will conduct the appointment over the phone. Most study activities can be conducted remotely (self-report assessments, quit smoking counseling, medication education) with the exception of medication dispensation and physical tests (breath/urine smoking bioverification and blood pressure). In these cases, we will mail participants their study medication so they can still receive their nicotine replacement medication as soon as possible rather than delaying their medication dispensation until they are able to attend an in-person visit.

*Cessation Visit 3 (TQD Day +14).* Participants will receive smoking cessation counseling and complete self-report assessments including any smoking since their last visit, and provide breath CO and urine nicotine/cotinine samples. Participants will be reminded to attempt to completely abstain from smoking and use of all nonmedicinal nicotine products. Participants will be encouraged to use their medication adherently and any medication problems such as side effects will be addressed. Participants will be reminded of the follow-up phone contact planned for 9 weeks post-TQD and the incentives for taking the call.

*Cessation Call 5 (TQD + Week 9).* Participants will receive a call on their final scheduled day of pharmacotherapy to assess smoking status, medication adherence, and assess any medication side effects. Participants will complete self-report assessments.

*Cessation Visit 4 (TQD > Week 9).* Participants who report abstinence from smoking at their Call 5 will be asked to attend an in-person visit for biochemical verification of abstinence (e.g., breath CO). Urine nicotine/cotinine levels will also be measured.

**Table 1. Study Visit Schedule and Procedures: Orientation and Precessation Phases**

Study Schedule, Assessment, and Procedures	Visit 1	Call 1	Call 2	Call 3
Study Phase	Orientation	Precessation		
Days +/- Target Quit Day: TQD	> -14	-12	-7	-3 to -1
Sign Informed Consent and HIPAA	X			
Inclusion/exclusion interview	X			
Smoking Status & Timeline Follow Back	X	X	X	X
Revised Wisconsin Smoking Withdrawal Scale (WSWS2-L)	X	X	X	X
Minnesota Tobacco Withdrawal Scale – Revised (MTWS-R)	X	X	X	X
Questionnaire of Smoking Urges (QSU)	X			
Demographics	X			
Smoking History	X			
Brief Wisconsin Inventory of Smoking Dependence Motives (Brief WISDM)	X			
Fagerström Test of Cigarette Dependence (FTCD)	X			
Wisconsin Predicting Patients' Relapse (WI-PREPARE)	X			
NIAAA Recommended Alcohol Questions	X			
Pain Numeric Rating Scale (PNRS)	X		X	
Graded Chronic Pain Scale (GCPS 2.0)	X			
Depression, Anxiety, Stress Scale (DASS21)	X			
Snaith-Hamilton Pleasure Scale (SHAPS)	X		X	
Distress Tolerance Scale (DTS)	X			
CO Breath & Blood Pressure	X			
Urine Collection	X			
Feedback Survey	X			
Interventions				
Counseling (in minutes)				15-25

**Table 2. Study Visit Schedule and Procedures: Cessation Phase**

Study Visit Schedule, Assessment, and Procedures	Call 4	Visit 2	Visit 3	Call 5	Visit 4
Study Phase	Cessation				
Days +/- Target Quit Day: TQD	+ 1-2	+ 7	+ 14	+ 63 (9w)	> 64 (>9w)
Smoking Status & Timeline Follow Back	X	X	X	X	X
Revised Wisconsin Smoking Withdrawal Scale (WSWS-2)	X	X	X	X	X
Minnesota Tobacco Withdrawal Scale – Revised (MTWS-R)	X	X	X	X	X
Questionnaire of Smoking Urges (QSU)	X	X	X		X
Pain Numeric Rating Scale (PNRS)	X	X	X	X	X
Depression, Anxiety, Stress Scale (DASS21)		X			
Snaith-Hamilton Pleasure Scale (SHAPS)	X	X	X	X	X
CO Breath & Blood Pressure		X	X		X
Urine Collection		X	X		X
Feedback Survey		X	X		
Interventions					
AE/Safety assessment			X	X	
Counseling (in minutes)	15	15	15		
C-NRT Adherence assessment			X	X	

### Self-Report Measures

WSWS-2. At all study visits participants will complete a newly revised set of Wisconsin Smoking Withdrawal Scale (WSWS2-L) items (Smith et al., in press). This 18-item assessment is intended to evaluate 6 subscales of craving, negative affect, difficulty concentrating, sleep difficulties, hunger, and restlessness. This assessment will provide data to validate a full version of the WSWS2-L. The brief 6-item version, the WSWS2-B, will be administered during EMA (see below).

**Assessment Battery.** Participants will complete a battery of self-report questionnaires using REDCap or Qualtrics on a computer or tablet at the Orientation Visits (see Table 1). A smaller assessment battery will be re-administered at subsequent study visits and calls (see Tables 1-2). Participants will complete several questionnaires designed to evaluate factors related to smoking experiences, nicotine dependence, and relapse risks. These questionnaires include the Minnesota Tobacco Withdrawal Scale-Revised (MTWS-R, (Hughes, n.d.), Smoking History Questionnaire, Brief Wisconsin Smoking Dependence Motives (Brief WISDM; Smith et al., 2010), Fagerström Test of Cigarette Dependence (FTCD; Fagerström, 2012), and Wisconsin Predicting Patients' Relapse (WI-PREPARE; Bolt et al., 2009). Participants will be asked a brief series of questions regarding menthol cigarette use, inhaled agents, noncombustible tobacco use, and e-cigarette use. Participants will complete a battery of assessments of affective and other personality traits, chronic pain, alcohol use, and psychiatric symptoms. These questionnaires include the Distress Tolerance Scale (DTS), Snaith-Hamilton Pleasure Scale (SHAPS; Snaith et al., 1995), Depression, Anxiety, and Stress Scale (DASS21; Lovibond &

Lovibond, 1995), Graded Chronic Pain Scale (GCPS 2.0), Pain Numeric Rating Scale (PNRS), and the NIAAA Recommended Alcohol Questions (NIAAA, 2003).

***Ecological Momentary (mobile) Assessment (EMA).*** Participants will provide daily ecological momentary assessment data (meaning data that has been collected “in the moment”) for 4 weeks total during the study (over 2 weeks of Precessation and 2 weeks of Cessation). Mobile online surveys technology using smartphones will be used to acquire data. For most of the EMA portion of the study, participants will complete 3 assessments per day (morning, midday, and evening). Daytime EMA prompts will be brief (10 min) to include the brief WSWS2-B focused on motivationally relevant affective/cognitive features of withdrawal (e.g., excluding sleep which will only be assessed at the evening EMA) and smoking (# cigarettes since last assessment). The evening assessment will include a larger battery of questionnaires to include the WSWS2-B and additional targeted assessments (see below). Versions of these EMA protocols have been used effectively in multiple large scale smoking cessation clinical trials over the past two decades with very high completion rates (~80%). The frequency of EMA will be increased for 5 days from 1-day pre-TQD to 3-days post-TQD in order to provide intensive monitoring of withdrawal symptoms on a more fine-grained time course during the early period of abstinence. During these 5 days participants will complete 6 EMA reports/day at within 2 hours of waking, waking + 3 hours, waking + 5 hours, waking + 7 hours, waking + 9 hours, and retiring. Participants will complete the full 18-item WSWS2-L (rather than the WSWS2-B) during the evening EMA during these 5 days (1x/day).

In addition to the WSWS2-B items, at each evening assessment (1x/day) or when a participant reports his/her first 3 post-TQD smoking events, they will also complete an expanded battery of EMA assessments regarding smoking, person-related, and contextual factors that day. These will include smoking (# cigarettes since last assessment), cessation self-efficacy, location (e.g., home, work, vehicle), activity (job, school, household), social context (e.g., social, work, stressful interaction), eating or drinking (e.g., eating, drinking caffeine, drinking alcohol), cigarette cues (e.g., lighter, ashtray, others smoking, tobacco ads), other inhaled substances (yes/no), cigarette availability (e.g., easy, hard, not available), medication use, pain (e.g., average, worst), smoking restrictions (e.g., home restriction, work restriction, public place restriction), with whom (e.g., friends, family, partner, co-worker), smoking triggers (e.g., see/smell cigarettes, stress, drink alcohol), tempted to smoke, coping strategies (e.g., cognitive, behavioral, none), and pre-coping intention.

**Table 3. Intensive Longitudinal Data Collection Schedule (Ecological Momentary Assessment: EMA)**

EMA and Medication Schedule	Precessation	TQD	Cessation	
	TQD -14 to -2	TQD-1 to TQD+3	TQD +4 to TQD+14	TQD +15 to TQD+21
Total: 5 weeks	13 days	5 days	11 days	7 days
# Daily Assessments	3/d	6/d	3/d	
Medication Status	no medication			C-NRT (Start TQD+8)

## Bio-verification Measures

*Carbon monoxide Assessment.* At all study visits, participants will provide expired breath sample of carbon monoxide (CO; Smokelyzer) for biochemical verification of abstinence. CO is used as both a measure of smoking heaviness at baseline as well as to confirm self-reported abstinence from smoking following the TQD. The higher of two samples recorded will be used as the value for data analysis. A cutoff of  $\leq 5$  ppm will be used as the criteria to be considered abstinent.

*Nicotine/Cotinine Assessment.* At all study visits, participants will provide a urine sample to assess nicotine/cotinine levels, which can be used to estimate smoking heaviness and environmental smoke exposure. Trained study staff at UW-CTRI will collect the participants' urine within the same day. All samples and test results will be labeled with the date of collection and the participant's numerical ID. Urine will be disposed of after nicotine/cotinine levels are read and recorded.

## Smoking Cessation

*Pharmacotherapy.* An 8-week supply of nicotine patch and nicotine mini-lozenges will be distributed at the visit 1-week post-TQD (Visit 2). Participants will be instructed to initiate C-NRT following the study visit on TQD +8-days. Nicotine patch and mini-lozenge dosing will be based off the 2008 PHS Clinical Practice Guideline and package insert with adjustments to account for the delayed start 1-week post-TQD. All participants will receive 2mg mini-lozenge due to the superior palatability of the 2mg lozenges. Participants are encouraged to use at least 5 mini-lozenges per day for the full 8 weeks. Participants who report any smoking or nicotine use (e.g., even a cigarette puff, e-cigarette use) in the 3 days before C-NRT distribution will receive 4 weeks of 14mg and 4 weeks of 7mg nicotine patches. Participants who report complete abstinence from smoking and nicotine in the 3 days before C-NRT distribution will receive 8 weeks of 7mg nicotine patches. This dosing schedule based on abstinence status is determined to balance the goals to ensure participants receive a sufficient dose of nicotine replacement while minimizing the likelihood of experiencing nicotine toxicity. The study staff will recommend dosage/use alterations as per good clinical practice if the participant experiences side effects.

Participants will be given the package insert use instructions and verbal guidance on medication use. Medication use will be assessed via evening EMA reports and at study phone calls. We will monitor adverse events at all study calls/visits as well as gather additional data on medication use. All participants will be given a phone number to call in case of medication issues or any other significant problems related to their participation.

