Study participants will be carefully monitored for side effects. Monitoring for these symptoms or conditions will be accomplished through assessment of adverse events (AEs) and serious adverse events (SAEs) at each study visit and phone contact during which the participants are receiving study medication. For all AEs and SAEs, study staff will take appropriate action to ensure the safety of the participant as follows: 1) Non-urgent AEs will be reported in a timely manner to study clinical staff (MDs); and 2) SAEs or AEs that raise concerns (e.g., allergic reaction; severe, unresolved changes in mood or any suicidal ideation) will be immediately reported to the study physician who will determine an appropriate course of action. In addition, participants will be given a telephone number to contact study staff in the event that participants have questions or concerns about study medication or medical/psychiatric reactions that may be related to study medication or participation, as well as instructions on when to seek emergency medical assistance. Individuals who report any significant mood change or suicidal ideation will be contacted immediately by a licensed staff psychologist or physician who will assess the level of risk and provide referrals as needed.

Pregnant women will not intentionally be recruited to the study. However, due to the longitudinal nature of the study, someone who was originally eligible for the study (not pregnant and agreed to take measures to avoid pregnancy) when they enrolled and then becomes pregnant will be allowed to continue participation (their choice) with the assurance that regardless, we will take actions to make sure she is permanently taken off study medication. She will still be allowed, if she chooses, to continue counseling and assessments for her remaining time in the study. Because the risks of the study medications to an unborn child are unknown, should a participant report that she has become pregnant, she will be advised to immediately stop using study

medications and to return any unused medications as safety precautions. No further medications will be given to this study participant while in the study. Study team members will be trained to respect and carry out the participant's wishes to stay or leave the study as they would any other participant.

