#### Data Safety Monitoring Plan

The Data Safety and Monitoring Plan (DSMP) for this research comprises not only the research conducted directly by the University of Wisconsin Center for Tobacco Research and Intervention (UW-CTRI) researchers, but also research conducted by other investigators collaborating with UW-CTRI-funded projects. All investigators must agree to comply with the procedures outlined in this DSMP.

*Monitoring the progress of trials and the safety of participants.* The Principal Investigator is responsible for routine monitoring of the trial's progress. This includes scheduled (biweekly during the first few months of the study and monthly thereafter) meetings with study staff and review of written documentation. Data reviewed at these meetings include the number and type of participants enrolled, the number and reasons for exclusions from enrollment, the number treated and the stage of intervention, summary of adverse events (AEs), individual review of serious adverse events (SAEs) and study participation, and outcome data. In addition, as noted above, SAEs or AEs that raise concerns (e.g., allergic reaction, significant change in mood or suicidality) will be immediately reported to the study physician who will determine an appropriate course of action. As data become available, the Study Director and Principal Investigator will review the data on a regularly scheduled basis (initially biweekly and later monthly) to determine progress.

To facilitate participant safety, study participants must meet study inclusion and exclusion criteria. Once enrolled, study protocols will assess the presence of AEs and SAEs at all study

visits and follow-up contacts. Should either excessive risk to study participants and/or convincing evidence of lack of measurable benefit to study participants be determined, the study will be stopped and all participants notified in a manner appropriate to the nature of the risk and/or lack of benefit. When taking that step the investigators will consult with the IRB and NHLBI.

*Plans for assuring compliance with requirements regarding the reporting of adverse events.* This DSMP requires that investigators notify NIH and the University of Wisconsin IRB in a timely manner (consistent with IRB and NIH policies) of the occurrence of any SAE or any AE which is severe, unexpected, and possibly related to study medication or protocol.

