Because this study involves pharmaceutical agents, if an unexpected SAE might be related to study drug use, both the Food and Drug Administration (FDA) and the manufacturer/supplier will also be notified within five days of investigators becoming aware of the event. The Principal Investigator will assist the study medication manufacturer/supplier in investigating any unexpected AE/SAE and will provide any follow-up information reasonably requested by the study medication manufacturer/supplier. Examples of SAE would be untoward medical or intervention occurrences that result in death, are life-threatening, require hospitalization or prolonging of existing hospitalization, create persistent or significant disability/incapacity, or involve congenital abnormality/birth defects.

Unanticipated problems will be monitored and reported to the DSMC. These are events that meet the following criteria: 1) suggest the research places subjects or others at increased risk of harm, 2) are unexpected (in terms of nature, severity or frequency) given the research procedures that are described in the study-related documents, and 3) possibly related to study participation. Any SAE will be queried and reported if it meets the definition of unanticipated problem. The Principal Investigator or designee will also be responsible for the accurate documentation, investigation and follow-up of all study-related adverse events. Adverse event assessment, recording, reporting, and investigation will be accomplished through staff training, structured/standardized assessments of untoward occurrences/events, and regular monitoring by study physicians and other study investigators. The Principal Investigator has ultimate responsibility for ensuring that SAEs are detected and reported in a timely manner. Additionally, the IRB will receive an annual report of all SAEs and AEs meeting the criteria listed above.

*Plans for assuring that any action resulting in a temporary or permanent suspension of an NIH-funded clinical trial is reported to the NIH grant program director responsible for the grant.* The NIH grant program director will be notified within five days if the Principal Investigator deems it necessary to suspend the clinical trial. In the case of a temporary suspension, the Principal Investigators will develop a plan for continuation of the study and discuss this plan with the NIH grant program director in a reasonable time frame.

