**Table 2. Study Visit Schedule and Procedures: Cessation Phase**

Study Phase	Cessation				
	Call 4	Visit 2	Visit 3	Call 5	Visit 4
Days +/- Target Quit Day: TQD	+1-2	+7	+14	+63 (9w)	>64 (9w)
CO Breath, Urine, & Blood Pressure		X	X		X
Smoking Status & Timeline Follow Back (TLFB)	X	X	X	X	X
Revised Wisconsin Smoking Withdrawal Scale - Long (WSWS2-L)	X	X	X	X	X
Minnesota Tobacco Withdrawal Scale – Revised (MTWS-R)	X	X	X	X	X
Questionnaire of Smoking Urges (QSU)	X	X	X	X	X
Snaith-Hamilton Pleasure Scale (SHAPS)	X	X	X	X	X
Pain Numeric Rating Scale (PNRS)	X	X	X	X	X
Depression, Anxiety, Stress Scale (DASS21)		X			
Interventions					
Counseling (in minutes)	15	15	15		
Medication Education/Dispensing		X			
Medication Adherence/AEs			X	X	

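### The protocol conflicts with itself on whether adverse events are asked about at Call 4 and Visit 2, the two contacts in the unmedicated quit week

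*Protocol*

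**What the plan says.** Three places in the protocol use wide wording. The pharmacotherapy text under Smoking Cessation states: "We will monitor adverse events at all study calls/visits as well as gather additional data on medication use". The Data Safety Monitoring Plan states: "Once enrolled, study protocols will assess the presence of AEs and SAEs at all study" visits, and it adds follow-up contacts. The same plan relies on "structured/standardized assessments of untoward occurrences/events" and requires notification of "any AE which is severe, unexpected, and possibly related to study medication or protocol", so an event need not be drug-related to be reportable.

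Other places are narrower. Under Adequacy of Protection Against Risks, the Protection Against Risk text places AE and SAE assessment "at each study visit and phone contact during which the participants are receiving study medication". In protocol Table 2 the row "AE/Safety assessment" is marked at Visit 3 and Call 5 only. In SAP Table 2 the row "Medication Adherence/AEs" is marked at the same two contacts. Table 1, which covers the orientation and precessation contacts, has no AE row in either document.

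Combination nicotine replacement starts at TQD+8, the day after Visit 2, and runs to TQD+63.

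**The concern.** The first week after the quit day is the design's deliberate departure from usual practice. The Potential Risks text says participants will be told that nicotine replacement is normally started on or before the quit day. The delay is therefore an exposure created by the protocol, and the Data Safety Monitoring Plan asks for events possibly related to the protocol as well as to the drug. Staff who work from the schedule would ask no general AE question in that week. Staff who work from the wide wording would ask at both contacts.

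What is at stake is the safety record. If the schedule was followed, a medical event in the first week that the other measures do not pick up would reach the investigators and the six-monthly committee review only if the participant volunteered it, or if the Visit 3 question looked back that far. An empty first week in an AE summary could then mean either that nobody reported an event or that nobody was asked.

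**Working it through.** No figure in the plan needs reproducing. The check sets the rules beside each cessation-phase contact.

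| Contact | Day | On study medication? | Required by the wide wording? | Required by the on-medication rule? | Marked in Table 2 (protocol / SAP)? |
|---|---|---|---|---|---|
| Call 4 | TQD+1 to +2 | No | Yes | No | No / No |
| Visit 2 | TQD+7 | No (dispensed, started next day) | Yes | No | No / No |
| Visit 3 | TQD+14 | Yes | Yes | Yes | Yes / Yes |
| Call 5 | TQD+63 | Yes (last scheduled day) | Yes | Yes | Yes / Yes |
| Visit 4 | after TQD+63, only if abstinence is reported | No | Yes | No | No / No |

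**Step 1.** The dosing window is TQD+8 to TQD+63. Visit 3 and Call 5 fall inside it; Call 4 and Visit 2 fall before it. The on-medication rule names no contacts, so this mapping is inferred from the dosing dates.

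**Step 2.** Marked on-medication contacts: 2 of 2. Marked contacts in the unmedicated quit week: 0 of 2. Both tables follow the on-medication rule and depart from the wide wording.

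**Step 3.** The contact descriptions under Cessation Phase agree with the tables. Side effects are mentioned at Visit 3 and Call 5. The Call 4 and Visit 2 descriptions list counseling, self-report and smoking since the quit day or last visit, and Visit 2 adds breath and urine samples and dispensing. Neither lists AEs.

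**Step 4.** What does cover the first week:

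- counseling of about 15 minutes at both contacts, audio recorded, by counselors whom licensed psychologists supervise;
- the withdrawal scales and the pain rating at both contacts, plus the mobile assessments;
- the DASS21 and blood pressure at Visit 2;
- a phone number for medication issues or other significant problems related to participation;
- immediate contact by a psychologist or physician when mood change or suicidal ideation is reported;
- replacement of a missed Visit 2 or Visit 3 by a phone appointment.

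The scales ask about set symptoms, and the phone line and escalation depend on the participant raising the matter. None is a scheduled general AE question.

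**Step 5.** Neither document gives a recall window for the Visit 3 AE question, so the documents cannot show whether it reaches back into the first week.

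**The case against.** The strongest reply is that an on-medication plan is reasonable. No study drug is given in the first week, the protocol regards withdrawal as a minimal health risk, and it attributes the study's risks chiefly to the nicotine replacement. That would be a fair reason for a narrower rule. But the protocol does not adopt it consistently: two sections promise assessment at all contacts.

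A second reply is that the tables are summaries and weak evidence of omission. This has some force. Protocol Table 1 shows counseling under Call 3, while the text and SAP Table 1 put it at Call 2. Protocol Table 2 has no dispensing row, and the QSU entry at Call 5 differs between the documents. The AE row also sits beside medication adherence and may be a side-effect form. However, the two AE rows agree with each other, with the contact descriptions and with the on-medication rule. If the row is only a side-effect form, the general assessment has no place in either schedule.

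Four stronger readings are tempting and are not supported:

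- **That AEs were not asked about in the first week.** The wide wording requires them at both contacts. The documents conflict; they do not establish absence.
- **That 2 of 8 post-enrollment contacts is the size of the gap.** That count adds Calls 1-3, when participants smoke as usual without study drug, and Visit 4, which only participants reporting abstinence attend. The relevant count is 0 of 2.
- **That anyone who misses Visit 3 goes unasked until TQD+63.** The protocol replaces a missed Visit 3 with a phone appointment.
- **That a number of uncovered days can be stated.** Any such number depends on an assumed Visit 3 recall window, and it is zero if that window reaches back to the quit day.

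**Conclusion.** The point holds as a conflict between two safety rules in the current text. Its size is 0 of 2 marked contacts in the unmedicated quit week, against 2 of 2 on medication. This rests on the TQD+8 to TQD+63 dosing window and on the AE rows as they stand in both Table 2 schedules. It is more than missing detail, because following the schedule breaks the commitment in the Data Safety Monitoring Plan.

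The consequences are limited to safety ascertainment and reporting. The SAP specifies no AE analysis, and no efficacy or psychometric result changes. The SAP says follow-up was complete by September 21, 2022, so no decision on continuing this sample is open. The documents show neither a missed event nor which rule staff followed.

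**What to change.** **Protocol and schedules.** Remove the on-medication limit from the Protection Against Risk text. Mark AE/safety assessment at Call 4 and Visit 2 in Table 2 of both documents. State the recall window: since the TQD at Call 4, and since the last contact from Visit 2 onward. Call 4 then covers the TQD to the call, Visit 2 covers the rest up to TQD+7, and Visit 3 continues from there, so the unmedicated week is fully covered. The cost is one short item at two contacts that already take place, plus some extra logging of minor events. Adding the item at Calls 1-3 and Visit 4 is optional; it would meet the wide wording literally.

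**Completed sample.** The safety report should state at which contacts AEs were asked and over what recall window. If the first week was not covered, limit AE statements to TQD+8 to TQD+63, and narrow the wording in the pharmacotherapy section and the Data Safety Monitoring Plan to match, with a reason. This costs only text. Answers that were not collected cannot be recovered.
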